7.2 Efficacy outcomes

7.2.1 Procedure pain/discomfort

A secondary endpoint is the tolerability of the procedure. Current intensity of pain/discomfort is verbally provided by the participant during the procedure for each treatment location and overall immediately post procedure. Pain/discomfort is assessed using the 11-point NPRS where 0 indicates no pain/discomfort and 10 indicates the worst pain/discomfort imaginable.¹

The count and percentage of participants indicating pain and the mean \pm SD pain score will be calculated. The termination of any procedure due to pain will also be noted.

7.2.2 Reflective Total Nose Symptom Score (rTNSS)

A secondary efficacy endpoint is the mean change from baseline in the rTNSS at the 30-day and 90-day follow-up periods. The rTNSS is a PRO used to describe symptoms of rhinitis.² The assessment consists of 4 nasal symptom domains (runny nose [rhinorrhea], itchy nose, sneezing, and stuffiness [nasal congestion]). Each item is rated from 0 (absent) to 3 (severe). The 4 domains are added together to provide an overall score ranging from 0 to 12.

The mean \pm SD for the change from baseline to the 30-day and 90-day follow-ups in the rTNSS will be calculated within subjects (paired observations). Significance of the change from baseline will be assessed using a paired *t*-test with (2-sided) 0.05 alpha level indicating significance. If the data are not normally distributed, a Wilcoxon signed rank test will be conducted in place of the *t*-test and the median and interquartile range will be presented instead of the mean \pm SD. Normality will be assessed by the Shapiro-Wilk test, where a *p*-value <0.05 indicates the non-normality of the data.

Additional exploratory calculations may include:

- Count and percentage of participants with any improvement (≥ 1 -point)
- Count and percentage of participants with rTNSS improvements of $\geq 25\%$, $\geq 30\%$, and $\geq 50\%$.
- Evaluation of individual rTNSS domain scores (rhinorrhea, congestion, itching, and sneezing)
- A subscale derived as the sum of the rhinorrhea and nasal congestion components

It is anticipated that changes in the nasal congestion and the runny nose scores of the rTNSS will be more impacted than the itching and sneezing scores and, therefore, will be of more interest for additional analysis.

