## 9.4 STATISTICAL ANALYSES

### 9.4.1 GENERAL APPROACH

All statistical analyses will be performed using a two-sided hypothesis test at the overall 5% level of significance. P-values will be rounded to three decimal places. If a p-value is less than 0.001 it will be reported as "< 0.001." If a p-value is greater than 0.999 it will be reported as "> 0.999." No adjustments for multiplicity are planned.

Continuous data will be summarized using descriptive statistics: n, mean, standard deviation or standard error, median, minimum and maximum. The decision to use either standard deviation or standard error will be based upon the objective of the presentation: standard deviation will be used when the interest is the natural variability of the data; standard error will be used when comparing two or more means. Continuous variables that are recorded using approximate values (e.g., < or >) will be replaced by the closest exact value for the calculation of summary statistics.

Categorical variables will be summarized using frequency counts and percentages.

For ordinal-scaled variables, a combination of the above may be employed as appropriate: frequency and percentage of observations within a category and means and standard deviations of the scores of the categories.

For categorical and ordinal variables, percentages will be calculated based on non- missing data.

All analyses will be based on available data; no imputation for missing data will be conducted.

Baseline is defined as the last measurement for the outcome of interest obtained before the exposure to the study device.

Duration variables will be calculated using the general formula: [(end date – start date) +1]

Within-subject changes will be calculated as visit value minus baseline value such that a negative change reflects a decrease and a positive change signifies an increase. No judgment (“better” or “worse”) is associated with the sign of the change, only direction. The Wilcoxon Signed Rank test will be used to test the null hypothesis that the mean (or median) within-subject change is equal to zero.

---

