#### 9.4.2 ANALYSIS OF THE PRIMARY EFFICACY ENDPOINT(S)

For the purposes of formality, rTNSS has been designated as the primary efficacy endpoint. However, since this is, in fact, a feasibility study, any of the secondary endpoints described below may be promoted in the next study to primary status. Therefore, the analytical approach for all efficacy endpoints will be identical.

The objective of these analyses is to present the changes from baseline for a small sample size in a manner that is statistically sound and intuitively comprehensible. To that end the tables will present summary statistics for the Baseline, 7-Day, and 1- and 3-Month timepoints, as well as serial changes from baseline.

The statistical null hypothesis is that the deltas are distributed around zero change. Wilcoxon Signed Rank tests will be employed to evaluate whether the deltas are distributed around zero or shifted either positively or negatively away from zero. No adjustments for multiplicity are planned since this is a feasibility or proof of concept study.

---

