#### 9.4.3 ANALYSIS OF THE SECONDARY ENDPOINT(S)

The secondary endpoints are changes over time in:

- NOSE Survey
- SNOT-22
- MiniRQLQ
- VAS – nasal symptoms
- CGI-I
- Physician Assessment of congestion
- Physician Assessment of turbinate hypertrophy

The analytical approach is described in the section above for the Primary Endpoint.

---

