7.3.1 Nasal Obstruction Symptom Evaluation

The NOSE scale is a validated PRO instrument that allows participants to quantify their perception of nasal obstruction.⁴ The tool measures the severity of 5 symptoms (nasal congestion

or stuffiness, nasal blockage or obstruction, trouble breathing through the nose, trouble sleeping, and difficulty breathing through the nose during exercise or exertion) on a Likert scale from 0 (no problem) to 4 (severe problem). The sum of the 5 symptom scores is multiplied by 5 to give a score range from 0 to 100.

Lipan and Most developed a clinically relevant classification system for NOSE scores: mild (5-25 points), moderate (30-50 points), severe (55-75 points), or extreme (80-100 points).⁵ This system has been used to define treatment responders. In previous clinical studies, responders were defined as participants who had at least 1 NOSE class improvement or a NOSE score reduction of at least 20% from baseline.

The mean \pm SD for the change from baseline to the 30-day and 90-day follow-ups in the total NOSE score will be calculated for matched pairs. Significance of the change from baseline will be assessed using a paired *t*-test with (2-sided) 0.05 alpha level indicating significance. If the data are not normally distributed, a Wilcoxon signed rank test will be conducted in place of the *t*-test and the median and interquartile range will be presented instead of the mean \pm SD. Normality will be assessed by the Shapiro-Wilk test, where a *p*-value <0.05 indicates the non-normality of the data.

The count and percentage of participants who meet the NOSE responder definition will be calculated using the previously used definition of NOSE responder (see above). Individual NOSE symptom scores may also be analyzed.

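### Protocol and SAP prescribe different tests for the efficacy changes, and the SAP's normality gate can drop the rTNSS mean change and SD from the tables (minor)

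*SAP*

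**What the plan says.** **Test.** Protocol 9.4.2 states that "Wilcoxon Signed Rank tests will be employed to evaluate whether the deltas are distributed around zero" or shifted away from it, with no normality condition. It gives a reason for uniformity ("any of the secondary endpoints described below may be promoted in the next study to primary status") and continues: "Therefore, the analytical approach for all efficacy endpoints will be identical". Protocol 9.4.3 carries this to the secondary endpoints: "The analytical approach is described in the section above for the Primary Endpoint".

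**Summary.** Protocol 9.4.1: "Continuous data will be summarized using descriptive statistics: n, mean, standard deviation or standard error, median, minimum and maximum". Mean and median stand together, and nothing in the data switches one off.

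**SAP.** Section 7.2.2 opens: "A secondary efficacy endpoint is the mean change from baseline in the rTNSS at the 30-day and 90-day follow-up periods". It calculates the mean and SD of the change and tests it with a paired t-test at two-sided 0.05. If Shapiro-Wilk gives p<0.05, Wilcoxon replaces the t-test and "the median and interquartile range will be presented instead of the mean" and SD. The same gate stands in 7.3.1 ("If the data are not normally distributed, a Wilcoxon signed rank test will be conducted in place of the" t-test) and in 7.3.2 to 7.3.4, so it covers rTNSS, NOSE, SNOT-22, VAS and mini RQLQ. The SAP does not say whether normality is judged separately at each visit. Its section 11 concerns SAP versions only, and no SAP section records the departure from the Protocol.

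**Alpha.** Protocol 9.4.1 puts its two-sided tests at an overall 5% level and, in the same paragraph, plans no multiplicity adjustment. SAP 10.5 plans none either, and SAP 10.7 says that overall type 1 error is not controlled.

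**The concern.** An analyst cannot follow both documents. Under the Protocol the test is fixed and both summaries appear. Under the SAP the test and the printed summary depend on the result of a preliminary test on 30 observations.

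The practical stake is reporting. The Protocol expects that an endpoint from this study may become primary in the next one. The mean change and its SD are the usual inputs for sizing that study, and the SAP wording allows them to be left out for the endpoint that it describes as a mean change. If the gate is run per visit, Day 30 and Day 90 could be summarised on different scales. rTNSS is the exposed measure because it takes whole-number values from 0 to 12: ties alone push Shapiro-Wilk towards rejection.

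The alpha phrase is a separate, smaller matter: the Protocol claims a property that its own unadjusted plan does not have.

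**Working it through.** **1. The stated level.** Read per test, the Protocol's 5% is simply the level of each comparison and agrees with SAP 7.2.2. Read as overall it is not reproduced. For the two rTNSS tests (Day 30, Day 90), both nulls true and independent: 1 − 0.95² = 1 − 0.9025 = 0.0975, or 9.75%. By simulation the figure is about 9% at a between-test correlation of 0.5 and 7.1% at 0.9. None is 5%.

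**2. How often the gate fires for rTNSS.** Inputs:
- n = 30 (Protocol 9.2, SAP 3.1.3).
- Mean change about −3.1, from FROST in Protocol 2.3: 3.06 − 6.15 = −3.09 at 30 days and 3.02 − 6.15 = −3.13 at 90 days.
- The documents give no SD of change, so SDs of 1.5, 2, 2.5 and 3 are assumed, with between-visit correlation 0.5 or 0.8, also assumed.
- Change = round(Normal(−3.1, SD)), two visits, 5,000 trials per setting. The gate fires if Shapiro-Wilk p<0.05.

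| Assumed SD | Fires at a given visit | Fires at one or both visits (corr. 0.5 / 0.8) | Visits summarised differently (corr. 0.5 / 0.8) |
|---|---|---|---|
| 1.5 | 44–45% | 69.0% / 65.4% | 48.6% / 42.5% |
| 2 | about 21% | 37.1% / 36.3% | 32.7% / 30.3% |
| 2.5 | 12–13% | 23.2% / 23.5% | 21.6% / 20.8% |
| 3 | 9–10% | 18.2% / 17.9% | 17.1% / 16.2% |

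The last two columns apply only if the gate is run per visit. Consistency check for SD 1.5, correlation 0.5: the visit rates are 0.449 and 0.445, so both fire in 0.449 + 0.445 − 0.690 = 0.204, and the visits differ in 0.690 − 0.204 = 0.486, as tabulated.

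The excess over 5% comes from rounding: unrounded normal changes fire in about 5%. Imposing the 0 to 12 limits (SD of change about 1.9 to 2.5, assumed) gives 13–22%. Strong skew (gamma, shape 2; SD 2 to 3) gives 75–93%.

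**3. Other scales** (assumed SDs). NOSE fires in 7–10%, and SNOT-22, VAS and mini RQLQ in 5–6%. The problem is mainly rTNSS.

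**4. Does the switch alter the verdict?** At mean −3.1 with rounded normal changes, t and Wilcoxon agreed in every trial (3,000 per SD). With symmetric changes and a true mean of zero, the gated rule rejects in 4.7–5.5%. With skewed changes (gamma, shape 2, rounded) and a true mean of zero, Wilcoxon and the gated rule reject in about 8–9% and the t-test in about 6–7%. The Wilcoxon excess arises because it does not test the mean.

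**5. Price of a fixed Wilcoxon test.** Power at an assumed mean of −1 with normal changes, t / Wilcoxon, for SD 1.5 to 3: 93.7 / 93.1, 74.3 / 72.5, 56.3 / 55.4, 42.0 / 41.1%. The loss is 0.6 to 1.8 percentage points.

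**The case against.** **The mean may not be lost.** Protocol 9.4.1 and 9.4.2 already call for mean and median and for tables of changes from baseline, and the SAP does not rescind them. SAP 7.2.2 also says that the mean and SD will be calculated. This stands in part: the loss occurs only if the SAP's replacement wording governs the tables. But the text does not say which document governs, and the two instructions cannot both be followed.

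**The endpoint is not always a mean.** SAP 3.1.1 and 3.1.2 speak only of change, and Protocol 9.4.1 allows mean or median in its null hypothesis. This stands: the internal conflict lies in SAP 7.2.2, not in every statement of the endpoint.

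**Wilcoxon is not clearly better.** Under skew it is further from 5% than the t-test as a test of the mean. This stands: the choice of test is a judgement. The need is for one test, fixed in advance, in both documents.

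**Stronger readings to avoid.**
- A reader might infer that counts-only reporting of CGI-I (SAP 7.3.5) and of the endoscopy grades (SAP 7.2.3) are further breaches of Protocol 9.4.3. CGI-I has no baseline value to subtract, so a test of change from baseline cannot be run on it. Protocol 9.4.7 already plans cross-tabulation for visual severity, and SAP 7.2.3 may describe that image review.
- A reader might infer hidden error inflation from the overall 5%. Both documents openly plan no adjustment.
- A reader might infer that the gate biases the result. The simulations show no change of verdict at the FROST effect and, with symmetric data, no inflation.

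**Conclusion.** The conflict between Protocol 9.4.1 to 9.4.3 and SAP 7.2.2 and 7.3.1 to 7.3.4 is plain on the text. Its consequence is conditional: if the SAP wording governs, the rTNSS mean change and SD may be absent from the tables at a given visit in about 45% (SD 1.5) down to 10% (SD 3) of trials, even with normal underlying changes. Those rates rest on assumed SDs and correlations and on whole-point rounding. The qualitative result survives the scale limits, and skew makes the gate fire more often.

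The primary safety endpoint is untouched. At the FROST effect the significance verdict does not depend on the test; near a true mean of zero with skewed data it can, which is a reason to fix the test beforehand rather than evidence for either one. The overall 5% is a wording error. Severity is minor: this is a single-arm feasibility study without a formal power calculation, and the harm is to consistency and to the usefulness of the report for planning.

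**What to change.** 1. **SAP 7.2.2 and 7.3.1 to 7.3.4:** delete the Shapiro-Wilk gate. State that n, mean, SD, median, IQR, minimum and maximum of the change will be presented at Day 30 and Day 90, whatever the distribution.
2. **Both documents:** name one pre-specified test. Either keep Wilcoxon, as the Protocol has it, with a table footnote that it does not test the mean; or keep the paired t-test and amend Protocol 9.4.1 and 9.4.2.
3. **Protocol 9.4.1:** describe the level as a nominal two-sided 5% per comparison, unadjusted, in place of the overall 5%.

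The cost is SAP wording, one Protocol phrase (plus the test wording in two Protocol sections if the t-test is kept) and simpler programming. If Wilcoxon is chosen and the changes are normal, the loss is at most about 2 percentage points of power. The alpha statement becomes less favourable but correct. No visit, procedure or data item changes.

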7.2.3 Quantitative nasal endoscopy scores

Endoscopic nasal examinations (before and after decongestant administration) will be performed at baseline and at the 30-day and 90-day follow-up visits. Photos will be taken of the middle and inferior turbinates (before and after decongestant). After deidentification and randomization, an independent physician, blinded to the participant and study visit, will review and grade each photo for 3 findings (inferior turbinate hypertrophy, middle turbinate hypertrophy, and nasal congestion). Each finding will be rated on a scale from 0 (none) to 3 (severe).³ Predecongestant and postdecongestant scores for each finding will be summarized using counts and percentages at baseline and the at the 30-day and 90-day visits.

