#### 9.4.7 EXPLORATORY ANALYSES

Visual severity of nasal congestion and turbinate hypertrophy will be evaluated for each side of the nasal cavity separately. Screening, 1- and 3-Month timepoint scores will be cross-tabulated, and the proportion with improvement will be calculated.

---

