3.1.1 Study Endpoints

The primary endpoint is the incidence of procedure-related serious adverse events (SAEs) and/or serious adverse device effects (SADEs)

Secondary endpoints are:

- Incidence of procedure-related adverse events (AEs) and/or adverse device effects (ADEs)
- Tolerability of treatment as rated by participant verbal report of pain/discomfort on the 11-point Numeric Pain Rating Scale (NPRS)
- Change from baseline in nasal symptoms using the reflective Total Nasal Symptom Score (rTNSS) at 30 and 90 days post treatment
- Change from baseline in nasal congestion and turbinate hypertrophy as assessed by nasal endoscopy 30 and 90 days post treatment

Additional exploratory analyses are:

- Procedural characteristics
- Physician evaluation of ease of treatment delivery using study device for inferior meatus location
- Change from baseline in patient-reported outcome (PRO) assessments at 30 and 90 days post treatment:
 - Nasal Obstruction Symptom Evaluation (NOSE)
 - Sino-Nasal Outcomes Test (SNOT-22)
 - Nasal symptom visual analog scale (VAS)
 - Mini Rhinoconjunctivitis Quality of Life Questionnaire (mini RQLQ)

- Physician assessment of participant change from baseline as measured by the Clinical Global Impressions – Improvement

All statistical analyses will be performed using SAS (version 9.4), unless otherwise noted.

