4.3 Analysis sets

There are 2 analysis populations:

- The safety population includes all participants who receive ClariFix treatment
- The efficacy population includes all participants who receive ClariFix treatment and have least 1 valid follow-up assessment

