10.4 Sensitivity and missing data analyses

Due to the small sample size and short-term follow-up, no sensitivity or missing data analyses are planned.

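### SAP 7.2.3 tabulates endoscopy grades visit by visit, so the SAP never computes its own secondary endpoint of change in congestion and turbinate hypertrophy.

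*SAP*

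**What the plan says.** SAP 3.1.1 lists as a secondary endpoint "Change from baseline in nasal congestion and turbinate hypertrophy as assessed by nasal endoscopy 30 and 90 days post treatment". SAP 7.2.3 describes how it is obtained. Photographs taken before and after decongestant are graded 0 to 3 by an independent physician, blinded to participant and visit, for inferior turbinate hypertrophy, middle turbinate hypertrophy and congestion. The analysis is one sentence: "Predecongestant and postdecongestant scores for each finding will be summarized using counts and percentages at baseline" and at the 30-day and 90-day visits. It gives no change score, shift table, proportion improved or test, and does not say how the left and right sides enter the counts.

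The efficacy population (SAP 4.3) is treated participants who "have least 1 valid follow-up assessment". SAP 10.4 says "no sensitivity or missing data analyses are planned".

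The protocol goes further in two places:

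- Section 9.4.3 lists physician-assessed congestion and "Physician Assessment of turbinate hypertrophy" among the secondary endpoints, to be analysed as in section 9.4.2, where "Wilcoxon Signed Rank tests will be employed to evaluate whether the deltas are distributed around zero".
- Section 9.4.7, headed exploratory, takes each side of the nose separately and says "Screening, 1- and 3-Month timepoint scores will be cross-tabulated, and the proportion with improvement will be calculated".

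**The concern.** The endpoint is a change within a person; the planned output is a set of cross-sectional distributions. Someone who follows the SAP to the letter will produce tables that do not contain the named endpoint. The SAP does not do this elsewhere: rTNSS, NOSE, SNOT-22, VAS and mini RQLQ (SAP 7.2.2 and 7.3.1 to 7.3.4) all get a change from baseline with a paired test. CGI-I is reported as counts, but it is itself a rating of change. So four exploratory scores get a paired analysis and this secondary endpoint does not.

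Two things are at stake. First, a shift in the group would be visible, but not how many participants improved or worsened. Second, the baseline and 90-day tables may cover different participants, so a shift caused by who still had images could be read as a treatment effect. In an open-label single-arm study this matters more for this outcome than for the others, because it is the only efficacy outcome in the SAP graded by a blinded independent reader. The rest are reported by the participant or rated by a site physician.

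**Working it through.** There is no stated figure to reproduce: the sample of 30 is a convenience sample (SAP 3.1.3), and neither document gives endoscopy grades. The check asks what the planned tables can and cannot determine.

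**Inputs.** Scale 0 to 3 (SAP 7.2.3); n = 30 (SAP 3.1.3). Grade counts are assumed, for one finding with one grade per participant and complete data at both visits:

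| Grade | 0 | 1 | 2 | 3 |
|---|---|---|---|---|
| Baseline | 2 | 8 | 14 | 6 |
| Day 90 | 6 | 12 | 9 | 3 |

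**Recoverable: the mean shift.** Baseline (8 + 28 + 18)/30 = 54/30 = 1.8. Day 90 (12 + 18 + 9)/30 = 39/30 = 1.3. Change −0.5.

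**Not recoverable: numbers improved and worsened.** Let B_k and F_k be the numbers with grade k or lower at baseline and day 90, with B and F equal to 0 below grade 0. B = 2, 10, 24, 30 and F = 6, 18, 27, 30.

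- Fewest improved = max(F_k − B_k) = max(4, 8, 3, 0) = 8 (27%).
- Most improved = 30 − max(B_k − F_{k−1}) = 30 − max(2, 4, 6, 3) = 24 (80%).
- Fewest worsened = 0, since F_k is never below B_k.
- Most worsened = 30 − max(F_k − B_{k−1}) = 30 − max(6, 16, 17, 6) = 13 (43%).

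**If nobody worsened.** The total fall is 54 − 39 = 15 grades, so at most 15 participants can have improved. That is attainable: 3 move from grade 3 to 2, 8 from 2 to 1 and 4 from 1 to 0, giving 6/12/9/3. The minimum is still 8: 22 unchanged, with 5 from grade 2 and 3 from grade 3 filling the 4 extra places at grade 0 and the 4 at grade 1. The range is 8 to 15 (27% to 50%).

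**The paired test is not recoverable either.** With assumed counts 0/10/12/8 at baseline and 3/12/10/5 at day 90, the arrangement with fewest improved (5 of 30) gives a signed-rank p of about 0.04, and the one with most improved (23 of 30) about 0.14 (normal approximation, zeros dropped).

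**Different participants at the two visits.** The pilot study lost 3 of 27 by 90 days (Protocol 2.3), which is 11.1%, or about 3.3 of 30. Assume 3 of 30 have a 30-day assessment but no 90-day images, 6 of 30 (20%) are grade 3 at baseline, and nobody changes. The day-90 table then shows:

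| Grade-3 participants lost | Day-90 grade 3 | Probability if loss is random |
|---|---|---|
| 0 | 6/27 = 22.2% | 2024/4060 = 49.9% |
| 1 | 5/27 = 18.5% | 1656/4060 = 40.8% |
| 2 | 4/27 = 14.8% | 360/4060 = 8.9% |
| 3 | 3/27 = 11.1% | 20/4060 = 0.5% |

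The larger FROST study kept 98 of 100 to 90 days (Protocol 2.3), which scales to 0.6 of 30 lost. With one missing, the day-90 figure is 6/29 = 20.7% or 5/29 = 17.2%.

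**The case against.** **The plan as a whole is not silent.** The protocol contains paired analyses, and its section 9.4.1 allows frequencies within category as a summary of ordinal data. True, and the gap is therefore in the SAP. But the SAP neither repeats nor cites those analyses, and permission to show frequencies does not turn them into a change analysis. The protocol text cannot simply be read across: 9.4.7 is exploratory, and 9.4.3 does not say whether its physician assessments are the site clinician's grades (8.3.1) or the optional independent image review (8.3.3).

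**No test is owed.** SAP 3.1.2 states a hypothesis only for rTNSS among the secondary endpoints. This stands, so a test can be optional. It does not excuse leaving out a paired description.

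**The 27% to 80% range is a mathematical bound on assumed grades.** Also true. Reaching 24 improved requires some of the others to worsen. The bound shows that the quantity is undetermined, not how wrong a reader would be. Excluding all worsening still leaves 27% to 50%.

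**Attrition may be trivial.** At the FROST rate the distortion is under 3 percentage points, and SAP 4.1 lists every discontinuation. This weakens the attrition argument, though images missing at an attended visit would not appear in that list. The main argument does not depend on attrition.

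**Side-level tables may not come free.** The example file label in Protocol 8.3.3 gives participant, visit and decongestant state but no side. That section does call for review of each side, so side should be recoverable, but this needs confirming.

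**Conclusion.** The concern holds for the SAP. Its only analysis of this secondary endpoint cannot yield the change that the endpoint names, and the protocol's paired analyses have been dropped without a stated reason. With complete data the mean shift survives; the numbers improved and worsened, and any paired test, do not. With missing images the mean paired change is lost as well.

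The size rests on assumed grade counts. In the illustration the number improved is undetermined between 8 and 24 of 30, or 8 and 15 if nobody worsened. The attrition effect is likely to be small: with three missing at random, about 91% of the probability (49.9% + 40.8%) lies at 18.5% or 22.2%, against a true 20%.

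This should be fixed but is not critical. The study is an uncontrolled feasibility trial with a safety primary endpoint, and no primary conclusion depends on it.

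**What to change.** In SAP 7.2.3, for each finding, decongestant state and side, add a baseline-by-30-day and a baseline-by-90-day shift table restricted to participants with images at both visits. Report the number and percentage improved by at least one grade, unchanged, and worsened by at least one grade, with the paired n. Keep the per-visit counts as supportive, and state how left and right enter them.

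A Wilcoxon signed-rank test is optional. If used, it should be at participant level, under a stated rule for combining the two sides, and should not treat them as independent. If it is left out, record the departure from Protocol 9.4.3 and say whether the physician assessments there meant the site grading or the image review.

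The cost is SAP wording and 3 findings × 2 decongestant states × 2 sides × 2 visits = 24 small 4×4 tables, which condense into one 24-row table of improved, unchanged and worsened. No new images or reader are needed, provided the grading record identifies the side. Making the change before the grades are analysed avoids choosing the summary after seeing the data.
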